The primary outcome variable is **adherence to MOUD**, quantified as the number of days MOUD was received as indicated during the last 4 weeks of the intervention period. We expect that this can be treated as a continuous variable in regression models. However, prior to modeling we will examine its distribution, to determine if this is appropriate. If, for example, we observe large ceiling effects (many participants report very high or perfect adherence) then we may model non-adherence as the number of days when MOUD was not received. In this case we expect it would have something similar to a Poisson distribution, possibly with over-dispersion which would suggest the use of negative binomial regression. The secondary outcome of **relapse** will be treated in two ways, as a binary indicator if any relapse during the last 4 weeks of the intervention period as determined by UDS or self-report, and the total number of self-reported days of use during the last four weeks of the intervention period. The first dichotomous outcome will require logistic regression. The second approach will depend on the observed distribution and may be treated as either negative binomial or continuous. The other secondary outcome, **cravings**, can be treated as continuous, which will also be true for the ancillary outcomes including depression, anxiety, and stress, are continuous variables.

The table below shows all other secondary measures and the instruments used to measure each of the variables. These instruments are also consistent with data harmonization efforts by the NIH HEAL Initiative. Data collection will happen in accordance with the timeframes stipulated above, T0 - T4. To examine within-subject and between-subject differences from pre to post intervention using repeated measures analysis of covariance (ANCOVA), including covariates, as necessary. Study outcomes will be also be examined using longitudinal regression models, including covariates, as necessary. The full model will include fixed within-subject effects to predict outcomes (stress, depression, anxiety, cravings, self-efficacy, baseline cortisol, cortisol reactivity).

Instrument	Construct	Instrument	Construct
Opioid Craving Scale	Craving	PROMIS Pain Intensity	Pain Intensity
Perceived Stress Scale	Stress	PROMIS Pain Interference	Pain Interference
Generalized Anxiety Disorder 7	Anxiety	PROMIS Pain Catastrophizing	Pain Catastrophizing

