Patient Health Questionnaire-9	Depression	Sleep Scale from the Medical Outcomes Study	Sleep
Community Assessment Index	Community Integration	Patient Global Impression of Change	Treatment efficacy
PROMIS Quality of Life	Quality of life	BPI Pain Severity	Pain Severity

**Cortisol Data Analyses:** This type of analysis will also be used in assessment of the cortisol data (i.e., stress reactivity) to examine the effects of treatment on baseline (resting) cortisol levels and cortisol reactivity. Cortisol data is often skewed, so transformations may be performed. The cortisol response will be quantified by calculating the area under the curve (AUC). The trapezoidal formula is given by:

$\sum_{i=1}^5 [t_i(m_i + m_{i+1}) / 2]$ , where  $t_i$  is the interval between sample  $i$  and sample  $i+1$  and  $m_i$  is the level of cortisol for sample  $i$ .

In addition, the influence of pre-treatment cortisol (resting and reactivity) on responsiveness to treatment (as measured by our primary outcome variables) will be examined.

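### The only cortisol response measure defined is total area from zero, so a change in resting cortisol alone would register as a change in reactivity

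*Combined protocol and SAP*

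**What the plan says.** The outcome-model paragraph of the MiMP R61 Analytic Plan lists, among the outcomes to be predicted, "stress, depression, anxiety, cravings, self-efficacy, baseline cortisol, cortisol reactivity". Cortisol Data Analyses keeps the same split. The analysis is meant "to examine the effects of treatment on baseline (resting) cortisol levels and cortisol reactivity", and a further analysis looks at "the influence of pre-treatment cortisol (resting and reactivity) on responsiveness to treatment".

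For measurement, the plan states "The cortisol response will be quantified by calculating the area under the curve (AUC") and prints one formula: the sum over i = 1 to 5 of t_i(m_i + m_{i+1})/2. Here t_i is the interval between consecutive samples and m_i is the cortisol level at sample i. That means six samples, five intervals and no baseline term. No area above baseline, peak-minus-baseline or slope is defined.

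Two other statements bear on this. Because cortisol is often skewed, the plan adds "so transformations may be performed". Outcomes are to be examined with "longitudinal regression models, including covariates, as necessary"; resting cortisol is not named as one of those covariates.

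**The concern.** The plan asks two questions of the cortisol data, one about resting level and one about the response to stress. Its single response measure mixes the two. A flat profile with no stress response still scores a positive value, and a uniform drop in level lowers the score.

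Three misreadings are possible when this AUC stands alone as reactivity:

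- A treatment effect on resting cortisol is reported as reduced stress reactivity.
- The AUC moves in the opposite direction to the true response.
- Pre-treatment AUC appears to predict treatment response when only resting level does.

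**Working it through.** The plan states no numerical cortisol result, so there is no figure to reproduce. The check is algebra on the printed formula, followed by illustrations on assumed values.

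**Algebra.** Write T for the sum of the t_i.

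- Replacing every m_i by m_i + c changes the sum by c × T, whatever the intervals.
- Equivalently, stated AUC = m_1 × T + area above the first sample. If sample 1 is the resting sample, the AUC contains the resting level multiplied by T.
- The area above the first sample, AUC − m_1 × T, does not change under the shift.

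**Assumed profiles.** Six samples 15 minutes apart (T = 75); rises above resting of 0, 2, 5, 4, 2, 1. Area of the rises = 15 × (0/2 + 2 + 5 + 4 + 2 + 1/2) = 15 × 13.5 = 202.5.

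| Profile | Stated AUC | Area above first sample |
|---|---|---|
| Resting 10 | 10 × 75 + 202.5 = 952.5 | 202.5 |
| Resting 8, same rises | 8 × 75 + 202.5 = 802.5 (−15.7%) | 202.5 (no change) |
| Resting 8, rises × 1.5 | 600 + 303.75 = 903.75 (−5.1%) | 303.75 (+50%) |
| Flat at 10 | 750 | 0 |

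The third row shows the sign reversal. A 20% fall in resting level alone lowers the stated AUC by 17.6%, 13.0% or 9.6% when the peak rise is 0.25, 1 or 2 times resting level.

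**Transformation.** Logging the samples first does not help. With rises 0, 1, 4, 5, 3, 1 on a resting level of 10, multiplying all levels by 0.8 moves the log-scale area from 189.9 to 173.2. The baseline-corrected log area stays at 17.2.

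**Simulation.** Assumptions: resting level and peak rise independent, means 10 and 5, error SD 0.5 per sample. SD pairs (resting, rise) were (3, 2.5), (3, 3), (4, 2.5), (4, 3) and, as a milder case, (2, 5).

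- *Correlations.* In the first four settings the stated AUC correlates 0.88–0.95 with resting level and 0.32–0.47 with true reactivity. At (2, 5) these become 0.59 and 0.80. The area above the first sample correlates 0.94–0.98 with true reactivity in all five.
- *Paired pre-post test at 5%*, resting lowered by 2, rise unchanged, pre-post correlation 0.5. The stated AUC shows a significant change in 26–40% of runs with n = 10 (equal allocation of 20) and 51–73% with n = 20. The area above the first sample does so in 4–6%.
- *Single predictor, n = 20*, resting level alone explaining 25% of outcome variance. The stated AUC alone is significant in 25–59% of runs. The area above the first sample alone, or the stated AUC with m_1 also in the model, is significant in 5–6%.

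**Where the problem disappears.** In a linear model holding both the untransformed AUC and the same m_1, at fixed sampling times, the two definitions give the same AUC coefficient and fit. In one check at n = 20 the coefficient (−0.00104), SE (0.00498) and R² (0.0229) were identical; only the m_1 coefficient changed (−0.046 against −0.124).

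**The case against.** The algebra is not in dispute; its reach and size are.

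**The plan never equates reactivity with the AUC.** True, but no other response measure is defined. If another was intended, reactivity has no definition, and the same clarification is needed.

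**The plan leaves a safe route open.** Its models allow covariates, and the predictor analysis mentions resting level and reactivity together. Fitted jointly, they avoid the problem for the AUC coefficient. The text does not say they will be, so the predictor part is an ambiguity that could resolve either way. Resting cortisol is also reported as its own outcome, which makes a misreading less likely but does not prevent one.

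**Sampling details may be stated elsewhere.** The plan refers to time frames T0–T4 set out above, which are not in the text available for review. The resting sample may be identified there.

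**The error rates depend on a large assumed effect.** This is fair. With a resting fall of 1 rather than 2, the paired-test rates drop to 10–14% (n = 10) and 15–26% (n = 20); with 0.5 they are 6–7% and 7–10%. With five completers and a fall of 2, the rate is 13–19%. A two-sample comparison of change at 10 per arm, with a fall of 2 in one arm, gives 15–26%. The n = 20 paired figure also needs all participants in both arms to share the same fall.

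**The corrected area is noisier than the main simulation suggests.** Also fair. At error SD 1.5 its correlation with true reactivity is 0.67–0.74 in the four main settings. With error SD 0.5 and extra SD 2 variation in sample 1, it is 0.59–0.65, and the corrected area correlates −0.34 to −0.46 with measured m_1. It still tracks reactivity better than the stated AUC in those settings, by a smaller margin.

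**Cortisol is not in Aim 1, its objectives or its hypotheses.** Correct. This limits what is at stake but does not repair the measure.

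**Conclusion.** The concern holds. Followed as written, the plan's only response measure can report a change in resting cortisol as a change in reactivity. That is certain from the formula, for any sampling intervals, whenever the AUC is analysed without same-session resting cortisol in the model.

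The size in this trial is unknown, because the documents give no cortisol levels, SDs or sampling times. Under the assumptions above, the false-signal rate runs from barely above 5% for a small resting shift to 40% at n = 10 for a shift of 2 units. The distortion is smaller where people differ more in response than in resting level. Reading the AUC as the reactivity measure is an inference, though the only one the text supports.

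The consequence is confined to the mechanistic cortisol analyses; adherence and feasibility are untouched. It should be fixed before the cortisol data are analysed.

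**What to change.** In Cortisol Data Analyses:

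1. State which sample is the pre-stressor resting sample. This comes first: if it is not sample 1, subtracting m_1 does not yield reactivity.
2. Define reactivity as the area with respect to increase: the stated sum minus the resting sample times the sum of the t_i. Alternatively, keep the stated sum and name the same-session resting sample as a covariate in every model that uses it as reactivity.
3. Keep the stated sum, labelled total cortisol output.
4. Do not log-transform the increase area, which can be negative. If raw samples are logged first, say that the target is then proportional rise.

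The cost is a sentence or two, using samples already planned. The increase area is a difference score: assay error or anticipatory variation in the resting sample adds noise and induces a negative correlation with measured resting cortisol. If that variation is expected to be large, the covariate version may be the better choice.
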